- e. For those subjects who are unable to continue participation in the study, but for whom consent is not withdrawn, an exit visit will be conducted as soon as possible.
- f. ie, 56 days to 3 days prior to vaccination.
- g. By telephone.
- h. Study-specific consent may occur on the day of vaccination, providing all required eligibility information has been collected through the ethics committee-approved hVIVO screening protocol.
- i. Directed physical examination includes respiratory system, nose, ear, throat, and facial lymph nodes examination.
- j. Supine systolic and diastolic blood pressure, heart rate and respiratory rate after at least 5 minutes rest.
- k. Supine ECG after at least 5 minutes rest.
- l. Neutralizing antibody to RSV-A Memphis 37b; blood will be collected within 90 days of vaccination and on entry to the Unit.

- m. For all female subjects.
- n. To include exclusion criteria 1, 7, 8, 9, 10, 14 and 16.
- o. The investigator must check for acute illness or body temperature ≥ 37.8 °C at the time of vaccination. In such cases, the subject may be re-screened (if vaccination number not assigned), or withdrawn at the discretion of the investigator. *Note*: the minimum time between vaccination and challenge is 24 days.
- p. Subjects will be closely observed for a minimum of 30 minutes post-vaccination. Any unsolicited, solicited local and systemic AEs, and vital signs will be documented by study-site personnel following this observation period.
- q. Unsolicited AEs will be collected from ICF signature until 28 days after vaccination, and from the entry into the Unit until 28 days after challenge.
- r. Rulers and thermometers will be distributed at the vaccination visit.
- s. Concomitant therapies will be collected and recorded in the eCRF from time of study vaccine administration until 28 days after vaccination, and from the entry into the Unit until 28 days after challenge, and additionally outside of these periods when associated with an SAE.
- t. Aliquots may be taken from nasal wash samples if more than one assay is to be assessed at a given timepoint.

ABBREVIATIONS

Ad26	adenovirus serotype 26
Ad35	adenovirus serotype 35
AE	adverse event
AUC	area under the curve
β -hCG	β -human chorionic gonadotropin
CI	confidence interval
COPD	chronic obstructive pulmonary disease
CS	circumsporozoite
DNA	deoxyribonucleic acid
DRC	Data Review Committee
ECG	electrocardiogram
eCRF	electronic case report form
eDC	electronic data capture
ELISA	enzyme-linked immunosorbent assay
ELISpot	enzyme-linked immunospot (assay)
ERD	enhanced respiratory disease
FA	full analysis
F protein	fusion protein
FDA	(US) Food and Drug Administration
FI	formalin-inactivated
FIH	first-in-human
GCP	Good Clinical Practice
HIV	human immunodeficiency virus
ICF	informed consent form
ICH	International Conference on Harmonisation
ICS	intracellular cytokine staining
IEC	Independent Ethics Committee
IFN γ	interferon gamma
IRB	Institutional Review Board
ITTc	intent-to-treat-challenge
PPI	per-protocol immunogenicity
PQC	Product Quality Complaint
RVAT	rapid virus antigen test
RSV	respiratory syncytial virus
RT-PCR	reverse transcriptase-polymerase chain reaction
SAE	serious adverse event
SAP	statistical analysis plan
SOP	standard operating procedure
SRP	study-responsible physician
SSC	subject symptom card
SUSAR	suspected unexpected serious adverse reaction
Th	T-helper (cell)
TNF α	tumor necrosis factor alpha
US	United States
VL-AUC	AUC for viral load
vp	viral particles
WBC	white blood cell

1. INTRODUCTION

A human adenovirus-vectored vaccine candidate which has shown promise in preclinical animal models of respiratory syncytial virus (RSV), and which is currently being tested in elderly subjects aged ≥ 60 years in stable health in Study VAC18193RSV1003, will be assessed in this study:

- Ad26.RSV.preF (JNJ-64400141), a replication-incompetent adenovirus serotype 26 (Ad26) containing a deoxyribonucleic acid (DNA) transgene that encodes for the pre-fusion conformation-stabilized F protein (pre-F) derived from the RSV A2 strain.

This will be an exploratory Phase 2a study where the prophylactic efficacy of Ad26.RSV.preF in the human challenge model of RSV infection will be assessed, and the appropriateness of the RSV human challenge model for RSV vaccine development will be evaluated on the basis of its ability to show a trend toward prophylactic efficacy with a RSV vaccine that has shown promise in preclinical challenge models.

For the most comprehensive nonclinical and clinical information regarding Ad26.RSV.preF, refer to the latest version of the Investigator's Brochure for Ad26.RSV.preF.¹

The term "sponsor" used throughout this document refers to the entities listed in the Contact Information page(s), which will be provided as a separate document.

1.1. Background

RSV is considered to be the most important cause of serious acute respiratory illness in infants and children under 5 years of age.^{16,34,38} Globally, in 2005, RSV was responsible for an estimated 3.4 million hospitalizations worldwide in children under 5 years of age. Furthermore, 66,000 to 199,000 children younger than 5 years died from RSV-associated acute lower respiratory tract infection (LRTI) in 2005, and 99% of these deaths occurred in developing countries.²⁷ Nevertheless, the disease burden due to RSV in developed countries is substantial, with RSV infection during childhood linked to the development of wheezing, airway hyperreactivity and asthma.^{31,33,35,36,37} In the United States (US), the infection rate was 68.8% in children younger than 12 months of age and 82.6% during the second year of life. Virtually all children had been infected at least once by 24 months of age, and about one half had experienced 2 infections.¹⁴ In the US, RSV infection in children under 5 years of age is the cause of 57,000 to 175,000 hospitalizations, 500,000 emergency room visits, and approximately 500 deaths each year.^{30,34,38} In children under 1 year of age, RSV is the most important cause of bronchiolitis, and RSV hospitalization is highest among children under 6 months of age.^{6,16}

In addition to children, RSV is an important cause of respiratory infections in the elderly, immunocompromised, and those with underlying chronic cardiopulmonary conditions.¹⁰ In long-term care facilities, RSV is estimated to infect 5-10% of the residents per year with significant rates of pneumonia (10 to 20%) and death (2 to 5%).¹¹ In one epidemiology study of RSV burden, it was estimated that 11,000 elderly persons die annually of RSV in the US.³⁹ These data support the importance of developing an effective vaccine for certain adult populations.

Despite the high disease burden, no licensed vaccine is available for RSV. The first vaccine candidate for young children, which consisted of formalin-inactivated RSV (FI-RSV), was associated with enhanced respiratory disease (ERD) upon infection with RSV.¹⁹ Although the mechanisms for ERD are not fully understood, it is thought that FI-RSV failed to induce adequate neutralizing antibody titers and CD8 priming, and induced a T-helper (Th) 2 skewed response.²⁶

Adenoviral-vectored Vaccines

It is thought that an efficacious RSV vaccine should induce high levels of neutralizing antibodies, antigen-specific CD8⁺ T-cell responses, and Th1-type CD4⁺ T cells.³ The candidate RSV vaccine being evaluated in this protocol is based on the AdVac[®] platform which has been shown to promote a strong antibody response, as well as CD8⁺ T cell and Th1-type CD4⁺ T-cell responses.

The immunogenicity profile of adenoviral vectors, with particular emphasis on Th1 responses, is illustrated by data obtained from immunization of adults with Ad26-vectored human immunodeficiency virus (HIV) vaccine (Ad26.ENVA.01), and of adults and infants with an adenovirus serotype 35 (Ad35)-vectored tuberculosis (TB) vaccine (Ad35.TB-S). These data show predominantly interferon gamma (IFN γ) and tumor necrosis factor alpha (TNF α) production in CD4⁺ and CD8⁺ T cells.^{2,5,29} Furthermore, in mice, Ad26- and Ad35-vectored vaccines with malaria circumsporozoite (CS) transgene inserts (Ad26.CS.01 and Ad35.CS.01), when administered as single immunizations or in combination as a heterologous prime-boost regimen at dose levels ranging from 1x10⁸ viral particles (vp) to 1x10¹⁰ vp, induce predominantly CD8⁺ T-cell responses, as well as mainly immunoglobulin (Ig) G2a antibody responses, indicative of a Th1-biased response.³²

Ad26.RSV.FA2 Clinical Data

Ad26 encoding for the wild-type RSV FA2, Ad26.RSV.FA2, has been evaluated in studies VAC18192RSV1001 and VAC18192RSV1003 (N = 48 and 32, respectively, of which 35 and 24 subjects, respectively, received Ad26.RSV.FA2) in adults at doses of 5x10¹⁰ vp. All subject visits have been completed in both studies.

Results indicate that there have been no safety concerns following vaccination in either study. After vaccination with Ad26.RSV.FA2, local reactogenicity comprised almost exclusively mild to moderate pain of median duration 1 to 3 days. The most commonly experienced solicited systemic adverse events (AEs; headache, fatigue, chills and myalgia) were also mostly mild to moderate in severity and of median duration 1 to 3 days; most unsolicited AEs and most laboratory abnormalities were mild to moderate in severity. No serious adverse events (SAEs) were reported and no AEs led to withdrawal from study vaccine.

Single vaccination with 5x10¹⁰ vp Ad26.RSV.FA2 raised humoral and cellular immunity; humoral and cellular immune responses were maintained for at least 6 months following

vaccination. An increase in RSV neutralizing antibody titers was observed; RSV-specific T-cell responses were also increased.

FA2 and preF RSV Vaccines

The candidate vaccine assessed in this study is Ad26.RSV.preF, ie, a replication-incompetent Ad26-containing a DNA transgene that encodes for the pre-fusion conformation-stabilized F protein derived from the RSV A2 strain.

First-in-human (FIH) clinical studies (VAC18192RSV1001 [FIH for Ad35.RSV.FA2] and VAC18192RSV1003 [FIH for Ad26.RSV.FA2]) have been completed with vaccines Ad26.RSV.FA2 and Ad35.RSV.FA2 (ie, a similar recombinant, replication-incompetent vaccine using an Ad35 vector), in which Ad26 and Ad35, respectively, encode for a wild-type RSV F protein of the RSV A2 strain.

The adenoviral vectors Ad26 and Ad35 are derived from Group B and D serotype adenoviruses and have been similarly modified to be replication-incompetent; expression of the antigen is controlled by the same promoter. An Ad26-based RSV vaccine was chosen for further clinical development over the Ad35-based counterpart based on a better immunogenicity profile from nonclinical data, a similar safety and immunogenicity profile but at half the Ad35 dose from clinical data, and a better manufacturing profile.

The F protein of RSV F undergoes a conformational transition from a metastable pre-fusion conformation to a stable post-fusion conformation. Neutralizing sensitive epitopes reside on both proteins, but recent evidence indicates that those epitopes specific to the pre-F protein seem to be more potent than those previously identified and present on the post-F protein.^{13,15} This evidence in the design of the candidate RSV vaccine (Ad26.RSV.preF) in which the adenoviral vector encodes for a full length RSV F protein stabilized in the pre-F protein conformation. **CCI**

[REDACTED]²² This change in the transgene confers more stability to the pre-fusion form of the protein.²² This change also induces higher immune responses against pre-fusion epitopes because the majority of neutralizing antibodies target the pre-fusion protein conformation.^{23,28} For these reasons, it is anticipated that the Ad26.RSV.preF vaccine candidate will generate more neutralizing antibodies relative to the Ad26.RSV.FA2 vaccine.⁴²

Ad26.RSV.preF Preclinical Data

Ad26.RSV.preF is immunogenic in mice and cotton rats, with humoral responses that include the induction of RSV neutralizing antibodies. In addition, in mice it was shown that Ad26.RSV.preF elicits cellular responses, characterized by the induction of RSV F-specific CD8⁺ IFN γ ⁺ T cells. The immune response after Ad26.RSV.preF immunization was Th1 biased. In cotton rats, single immunization with Ad26.RSV.preF protects the upper and lower respiratory tract from challenge with RSV A2 and RSV B strains, without induction of any histopathological signs of ERD.⁴²

Ad26.RSV.preF Clinical Data

Ad26.RSV.preF is under evaluation in the ongoing FIH Phase 1 study VAC18193RSV1003 in elderly subjects aged ≥ 60 years in stable health. In this randomized, placebo-controlled, double-blind study, 72 elderly male and female subjects have been randomized in parallel to one of five study groups and have received the first (Day 1) of two intramuscular injections as follows:

- Group 1 – 5×10^{10} vp Ad26.RSV.preF on Day 1 and 1 year later;
- Group 2 – 5×10^{10} vp Ad26.RSV.preF on Day 1 and placebo 1 year later;
- Group 3 – 1×10^{11} vp Ad26.RSV.preF on Day 1 and 1 year later;
- Group 4 – 1×10^{11} vp Ad26.RSV.preF on Day 1 and placebo 1 year later;
- Group 5 – placebo on Day 1 and 1 year later.

Safety and immunogenicity data from the unblinded interim analysis 28 days post-Dose 1 from all 72 subjects who received Ad26.RSV.preF (5×10^{10} vp or 1×10^{11} vp) or placebo confirmed the immunogenicity of the vaccine; the 1×10^{11} vp dose of Ad26.RSV.preF was more immunogenic than the 5×10^{10} vp dose. No safety concerns were revealed; the reactogenicity of both doses was comparable.

For study VAC18193RSV1003, Ad26.RSV.preF was provided in a different buffer (Formulation Buffer 1^a) from the one to be used in the current study (Formulation Buffer 2^b). The formulation buffer was changed to enhance the Ad26.RSV.preF drug product stability at 2 to 8 °C for storage purposes in future studies. The new formulation buffer was considered well-tolerated when tested in a nonclinical single-dose intramuscular safety study in rabbits.⁴²

Safety Data Supporting Dose Selection from Other Ad26-based Vaccines

In addition to the two completed studies with Ad26.RSV.FA2 and one ongoing study with Ad26.RSV.preF, the dose level for Ad26.RSV.preF used in this study is supported by experience in adults with other Ad26 vaccines encoding for different antigens (EnvA [in Ad26.ENVA.01 against HIV];^{4,5} CS protein [in Ad26.CS.01 against malaria];^{7,29} and Ebola glycoprotein [in Ad26.ZEBOV against Ebola virus]²⁵). Note that, in general, at a given dose level, no significant changes in the safety profiles of Ad26-based vaccines have been seen when the transgene has been changed.

In completed clinical studies,^c the safety of Ad26.ENVA.01, Ad26.CS.01 and Ad26.RSV.FA2 has previously been evaluated in at least 293 adult subjects, of whom 243 have received

^a CCI

^b

^c Safety data from these studies are summarized in a separate report (Adenoviral Vaccine Safety Database V2.0, December 2016) which is available on request.

5×10^{10} vp, and found to be well-tolerated. In addition, four Phase 1 studies with Ad26.ZEBOV have been completed in adults: 291 subjects have received Ad26.ZEBOV at 5×10^{10} vp and 1×10^{11} vp without significant safety issues: 15 subjects have received 1×10^{11} vp (25 doses administered), and 276 subjects have received 5×10^{10} vp. The safety data from these Ebola studies showed no safety concerns at 5×10^{10} vp and 1×10^{11} vp. Overall, these clinical data are supportive of dosing Ad26.RSV.preF at 1×10^{11} vp in the current study.

1.2. Overall Rationale for the Study

This is an exploratory, double-blind, randomized, placebo-controlled human challenge study in which healthy adult subjects will receive single intramuscular doses of 1×10^{11} vp of Ad26.RSV.preF or placebo and 28 days later (window between 24 to 90 days) will undergo intranasal challenge with RSV-A Memphis 37b virus. This is an exploratory study as an RSV vaccine has not previously been tested in this challenge model. The prophylactic antiviral effect, prevention of clinical symptoms of RSV infection, and prevention of RSV infection will be evaluated. The study will also explore the relationship between immunogenicity and efficacy outcomes.

The study is considered to be exploratory because no RSV vaccine has been previously tested in the human challenge model of RSV infection. The RSV vaccine developed by the sponsor is mainly intended to protect against moderate-severe low respiratory tract RSV infection. The RSV symptoms seen in this challenge model are mild and mainly limited to the upper respiratory tract compared to those which would be observed in a clinical efficacy trial of naturally-occurring infection where more severe symptoms, plus RT-PCR-confirmed RSV infection, would be measured (see [Attachment 4](#)). Although it might be expected that a vaccine would be better able to protect against mild disease than severe disease, it might also be that mild upper respiratory disease could be more difficult for a vaccine to protect against, for the reason that a parenteral vaccine would induce lower levels of antibody and cellular responses in the nasopharynx compared to levels induced in the blood and lower respiratory tract. Preclinical data indicates this might be the case: when the dose of vaccine is reduced, protection against virus infection in the nasopharynx is lost before protection in the lung. It is not known whether the vaccine in this study, which is to be dosed at the highest dose already given safely to humans, will induce a sufficient immune response to give protection in the nasopharynx, or at least to give an indication of some protection. Therefore this study is considered highly exploratory, and is as much a test of whether this model will prove to be useful in vaccine studies, as it is a study of the effectiveness the RSV vaccine under development.

Since preclinical models have suggested some level of protection by the vaccine against nasopharyngeal infection, the study includes a formal primary objective of lowering area under the curve of viral load (VL-AUC), despite the exploratory nature of this study. This VL-AUC has been found in previous studies to be the most sensitive and least variable parameter for efficacy measurement in this model. If the vaccine can prevent infection completely in some subjects, a powerful effect on the AUC would be seen since in those subjects the AUC would be 0. There are also a small number of secondary objectives related to reduction of symptoms

occurring at a specific time, reduction of overall mucous secretion and incidence of infection utilizing more severe or very mild symptoms as alternative definitions, coupled in both cases with two quantifiable RT-PCR measurements to confirm the symptoms are due to RSV.

The statistical approach to this exploratory study is to have an alpha of 20% to indicate a trend and 5% as a significant result for the primary endpoint. If positive results or a trend in the primary or secondary objectives are found, this would suggest that the challenge model may be a reasonable approach to examine vaccine efficacy and would provide evidence to perform more extensive studies. If this study fails its primary endpoint, and does not show any trends in the other endpoints, it would suggest that the human RSV challenge model is not an appropriate model to evaluate potential efficacy of RSV vaccines directed against more serious disease that has more of a lower respiratory component.

Therefore this study will serve as a pilot to explore the value of evaluating RSV vaccines in the human challenge model in RSV vaccine development, with the possibility that, if the model is appropriate, a trend toward efficacy with Ad26.RSV.preF could be detected.

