- PRIMARY ANALYSIS will be performed when all subjects have completed the quarantine phase or discontinued earlier. The pre-challenge neutralization and pre-F ELISA, and post-challenge RT-PCR, nasal mucous and tissue count, and clinical symptom data will be available although the analysis may be performed on snapshot data. All other data available at the time of primary analysis, including completed cellular data, will be included. Preliminary safety data, including Day 28 post-challenge, if available, will also be included.
- FINAL ANALYSIS will be performed when all subjects have completed the 6 month safety follow-up visit or discontinued earlier.

Depending on when the data are available, both analyses might be combined.

Efficacy Analyses

For the primary efficacy endpoint (VL-AUC of RSV-A Memphis 37b as determined by quantitative RT-PCR assay of nasal wash samples) the exact Wilcoxon Rank Sum test will be performed and the one-sided p-value will be interpreted at the 5% and 20% significance level, specifically only analyzing the statistical significance of a reduction in VL-AUC in the active versus placebo groups.

Secondary endpoints will be analyzed descriptively.

Immunogenicity Analyses

No formal hypothesis on immunogenicity will be tested. Descriptive statistics (geometric mean and 95% confidence interval [CI] for ELISA and virus neutralization assays; median and quartiles for ELISpot and intracellular cytokine staining [ICS]) will be calculated for continuous immunologic parameters at all

timepoints. For the humoral assays, geometric mean fold rises from baseline and corresponding 95% CIs may be calculated as well. For immunogenicity, baseline is considered as the last assessment pre-vaccination with Ad26.RSV.preF or placebo. Graphical representations of immunologic parameters will be made as applicable.

Frequency tabulations will be calculated for discrete (qualitative) immunologic parameters as applicable.

Safety Analyses

No formal statistical testing of safety data is planned. For the planned analyses, safety data will be analyzed descriptively.

TIME AND EVENTS SCHEDULE

Clinic Phase	Screening ^d	VACCINATION			VIRAL CHALLENGE: Quarantine Unit					OUTPATIENT			
					Pre-viral Challenge		Chall ^a	Post-viral Challenge		Dis-charge	Follow-up	Final Visit ^g	
Visit Timing		Vacc	Vacc +3 d ^b	Vacc +7 d	Vacc +26 d	Vacc +27 d	Vacc +28 d	Chall +1 d	Chall +2 d to +11 d	Chall +12 d ^c	Challenge + 28d	Vacc + 6 mo	

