11.2. Sample Size Determination

[figure not shown]
A sample size of 44 challenged subjects (22 vaccinated and 22 placebo subjects) was chosen as this would provide sufficient evidence to assess if the challenge model is a reasonable approach to examine vaccine efficacy. A multiple of 22 subjects was selected given the capacity of the quarantine Unit.

The sample size was based on the ability to detect trends with a high one-sided alpha (20%), given this is an exploratory study whose partial aim is to determine the utility of the RSV human challenge model for RSV vaccine development. Figure 2 shows the expected power for several reductions in VL-AUC of the quantitative RT-PCR assay, with this selected sample size, a mean VL-AUC in the placebo group of 320 log₁₀ h/mL with corresponding standard deviation 275, an infection rate in placebo of 65% and a one-sided alpha of 5% and 20% based on a Wilcoxon Rank Sum test. This graph suggests that for a one-sided alpha level of 20%, the study has at least 80% power if Ad26.RSV.preF induces a reduction of VL-AUC of the quantitative RT-PCR assay by 50% or more. For a one-sided alpha level of 5%, the study has at least 80% power if Ad26.RSV.preF induces a reduction of VL-AUC of the quantitative RT-PCR assay by 75% or more.

An effect that is significant at 5% (one-sided) will be considered a significant effect. An effect that is significant at 20% (one-sided) will be considered as a trend. This trend, if observed, might be confirmed in future studies.

As this is an exploratory study, the statistical assumptions described above will need to be demonstrated to be correct for the analysis to be conducted as indicated below and as planned in further detail in the SAP. For example, if the infection rate from the study is considerably below 65% then the study will be considered to be underpowered to be able to accurately determine the stated aims. The infection rate in the placebo group will be followed on an ongoing basis by an unblinded individual who does not have any other study function to ensure a sufficient infection rate has occurred. If the infection rate is lower than anticipated, additional subjects may be enrolled, initially four additional subjects in each arm and up to 70 in total. This is to ensure that a high enough number of evaluable subjects is reached in each arm.

Figure 2: Expected Power for Several Reductions in Viral Load

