11.4. Efficacy Analyses

For efficacy, baseline is defined as the last assessment challenge with the virus.

The **primary efficacy endpoint** is the VL-AUC of RSV-A Memphis 37b as determined by quantitative RT-PCR assay of nasal wash samples. The VL-AUC is calculated based on the viral load values measured twice daily, starting with the baseline value, and ending with the last available value before discharge.

For this primary efficacy endpoint the exact Wilcoxon Rank Sum test will be performed and the one-sided p-value will be interpreted at the 5% and 20% significance level, specifically only analysing the statistical significance of a reduction in VL-AUC in the active versus placebo groups.

The **secondary efficacy endpoints** are:

- The peak viral load of RSV-A Memphis 37b, defined as the maximum viral load as determined by quantitative RT-PCR assay of nasal wash samples, observed over the entire time period
- The effect of vaccination on viral load and symptoms on Day 6 and Day 7
- The viral load of RSV-A Memphis 37b as determined by quantitative RT-PCR assay of nasal wash samples over time
- The VL-AUC of RSV-A Memphis 37b as determined by quantitative culture of RSV of nasal wash samples and the corresponding AUC
- Weight of mucus produced over time and the corresponding AUC, tissue count
- Proportion of subjects with symptomatic RSV infection. Symptomatic RSV infection is defined in two ways:
 - Conservative: the subject has two or more quantifiable RT-PCR measurements on different samples **and** the subject has one of the following
 - symptoms from two different categories (Upper Respiratory, Lower Respiratory, Systemic) from the SSC, regardless of grade and assessment timepoint.
 - any Grade 2 symptom from any category.
 - Liberal: two or more quantifiable RT-PCR measurements plus any clinical symptom of any severity.

Note: the quantifiable RT-PCR assessment and the symptoms should not necessarily occur at the same day.

Exploratory efficacy endpoints are:

- Proportion of subjects with symptomatic RSV infection (RT-PCR or serology). Symptomatic RSV infection is defined as having two or more quantifiable RT-PCR measurements or serology confirmation of RSV, and any clinical symptom of any severity.
- Total clinical symptom score (using a composite of 10 and 13 self-reported symptoms on the SSC) over time and the corresponding AUC.

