6.2.1. Secondary and Exploratory Efficacy Endpoint Analysis

For viral loads of RSV-A Memphis 37b as determined by quantitative RT-PCR assay and by quantitative culture of RSV, number of observations, mean, standard error, median, first and third interquartile will be tabulated and means with standard errors will also be graphically presented per time point.

For clinical symptoms scores, total clinical symptom scores, mucus weight and number of tissues, number of observations, mean, standard error, median, first and third interquartile will be tabulated and means with standard errors will also be graphically presented per time point.

For peak viral load based on the quantitative RT-PCR assay, number of observations, mean, standard error, median, first and third interquartile will be tabulated for both groups and graphically presented with boxplots. Exact Wilcoxon Rank Sum tests will also be performed to compare the mean in the active versus placebo groups and the corresponding p-values will be presented. Note the study is only powered for the primary efficacy endpoint and not for any of the secondary one, interpreting these p-values should be done with caution.

For AUCs of viral loads, clinical symptoms and mucus weight, number of observations, mean, median, first and third interquartile (q1, q3) will be calculated for both groups and graphically presented with boxplots. Exact Wilcoxon Rank Sum tests will also be performed to compare AUCs in the active versus placebo groups and the corresponding p-values will be presented. Note the study is only powered for the primary efficacy endpoint and not for any of the secondary one, interpreting these p-values should be done with caution.

Descriptive statistics (number of observations, mean, standard errors, median, q1, q3) of values and changes from baseline for FEV₁, FVC, and FEV₁/FVC will be summarized at each scheduled timepoint. Mean with standard errors of actual values and changes from baseline will also be graphically presented. Finally, spirometry values that are below the clinically important limits, provided in the table below, will be classified as ‘abnormally low’ and the percentage of subjects with ‘abnormally low’ values will be summarized.

Parameter	Clinically Important Limits
FEV ₁	80%
FVC	80%
FEV ₁ /FVC	70%

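### A 'trend' in any secondary objective can support the challenge model, but 'trend' is defined only for the primary, and a null result comes with no interval on VL-AUC

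*Protocol*

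**What the plan says.** Protocol 1.2 describes the approach as "to have an alpha of 20% to indicate a trend and 5% as a significant result for the primary endpoint". Section 11.2 repeats the definition where it sizes the trial on VL-AUC: "An effect that is significant at 20% (one-sided) will be considered as a trend". Section 11.4 applies it to the exact Wilcoxon test of RT-PCR VL-AUC, where "the one-sided p-value will be interpreted at the 5% and 20% significance level". No section gives a threshold for any other endpoint.

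The next sentence of 1.2 goes wider. Its condition can be met on either tier of objectives: "If positive results or a trend in the primary or secondary objectives are found". What follows from that condition is hedged: "this would suggest that the challenge model may be a reasonable approach to examine vaccine efficacy". The same sentence also sees grounds for larger work. The opposite conclusion has its own condition: "If this study fails its primary endpoint, and does not show any trends in the other endpoints", the model would appear unsuitable for vaccines aimed at more serious disease. In Protocol 2.1.1, four of the five secondary efficacy objectives are framed as assessing a trend, and none says what would count as one.

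On analysis, the protocol synopsis (Efficacy Analyses) says "Secondary endpoints will be analyzed descriptively". SAP 6.2.1 goes further: "Exact Wilcoxon Rank Sum tests will also be performed to compare AUCs in the active versus placebo groups". This covers the viral-load, symptom and mucus AUCs, and a similar test is added for peak viral load. Neither sidedness nor a cut-off is given, although the SAP warns that only the primary is powered and urges caution. SAP Section 2 lists two changes, ECG tables and an RT-PCR sensitivity analysis, and does not mention these tests. AUCs are summarised by arm. The only efficacy intervals planned are for differences in the proportion with symptomatic infection.

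**The concern.** Judging the model is a stated partial aim of the trial, so the sentences in 1.2 are the nearest thing to its decision rule. The positive side is an either/or over several endpoints, and its key word has a meaning for only one of them. Either the one-sided 20% criterion carries over to the secondaries, and the chance of a spurious trend somewhere rises above 20%, or the secondary criterion is open and can be settled after the data are seen.

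The negative side has the opposite weakness. Absence of a trend is read as evidence about the model, yet nothing planned for VL-AUC would show whether the data exclude a useful effect or are merely imprecise. A vaccine with a modest effect and a vaccine with none could both be reported as showing that the model is unsuitable.

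**Working it through.** **Inputs.** From Protocol 11.2: 22 challenged subjects per arm, placebo mean VL-AUC 320, SD 275, placebo infection rate 65%, one-sided alpha 20% and 5%. The number of tests and their correlation are not in the documents; they are assumptions, varied below.

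**1. The plan's own figures.** Normal approximation with SE = 275 × √(2/22) = 82.9.
- 50% reduction (160), alpha 20%: Φ(160/82.9 − 0.842) = Φ(1.088) = 86%.
- 75% reduction (240), alpha 5%: Φ(240/82.9 − 1.645) = Φ(1.250) = 89%.

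Both agree with the stated minimum of 80%. Wilcoxon simulation with 35% zero AUCs in placebo, reading 320/275 as all placebo subjects, gives 82–90% for the first and 70–96% for the second, depending on distribution and on how the vaccine acts. With no effect, the single primary test rejects at about 20%, as intended.

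**2. How many tests.** P-values serving the primary or a clearly secondary objective: RT-PCR VL-AUC, peak viral load and mucus AUC, so three. Culture AUC makes four; it is exploratory in Protocol 2.1.2 but secondary in Protocol 11.4 and SAP 6.2. Symptom AUC, an exploratory endpoint, makes five. Counting objectives instead, the primary plus five secondary efficacy objectives gives six.

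**3. Chance of at least one false trend if every test is read at one-sided 20%.** Independent tests: 1 − 0.8^k. Equal correlation ρ: 1 − ∫ Φ((0.842 − √ρ·g)/√(1−ρ))^k φ(g) dg.

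| Tests k | Independent (upper bound) | ρ = 0.5 | ρ = 0.8 |
|---|---|---|---|
| 3 | 48.8% | 38.9% | 31.3% |
| 4 | 59.0% | 44.4% | 34.3% |
| 5 | 67.2% | 48.8% | 36.6% |
| 6 | 73.8% | 52.2% | 38.4% |

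A separate null simulation of the six objectives with shared infection status, using Fisher's exact test for the two infection definitions, gave 33–43%. Its subject-level correlations and symptom rates were assumed.

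**4. Effect of the undefined sidedness.** If secondary p-values are two-sided and read at 20%, each contributes 10% in the favourable direction. The independent upper bound is then 1 − 0.8 × 0.9² = 35.2% for three tests and 1 − 0.8 × 0.9⁵ = 52.8% for six.

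**5. A modest true effect, primary test alone.** For a 25% reduction (80) at alpha 20%, the normal approximation gives Φ(80/82.9 − 0.842) = 55%. Wilcoxon simulation (20,000 trials, gamma-shaped AUCs in infected subjects, 320/275 read as all placebo subjects) gives 58% if the vaccine scales AUC in infected subjects, 55% if it lowers the infection rate, and 56% if it does both. Reading 320/275 as infected subjects only gives 33–55%.

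**6. Could an interval settle a null?** Two-sided intervals matching one-sided 20% and 5% are 60% and 90%, with half-widths 0.842 × 82.9 = 69.8 and 1.645 × 82.9 = 136.4. With no true effect, the upper limit for the reduction falls below 160 with probability Φ((160 − 69.8)/82.9) = 86% and Φ((160 − 136.4)/82.9) = 61%. So at this sample size an interval can often rule out the effect the trial was sized for.

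**The case against.** The strongest reply is that the plan is openly exploratory and hedged. The 20% level is attached to the primary, the synopsis calls secondaries descriptive, SAP 6.2.1 urges caution with their p-values, Protocol 2.2 says the primary result itself needs careful reading and that a trend should be confirmed, and 1.2 speaks only of what results would suggest. Protocol 11.2 also treats a low infection rate as loss of power, so not every null would be read against the model. All of that stands. It limits the weight of the point, but it does not define a secondary trend or supply an interval for VL-AUC.

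Three stronger readings are tempting and are not supported.
- A reader might infer that the plan applies a 20% rule to every secondary, so that the true error rate is as high as 67% or 74% where 20% was promised. The documents set no secondary threshold and claim no error rate for the overall verdict. Those figures also need independent tests, which is implausible: RT-PCR AUC and peak come from the same samples, and both infection definitions require quantifiable RT-PCR.
- A reader might take the 42–45% miss rate at a 25% reduction as the plan's false-negative rate. It belongs to the primary test alone. The negative conclusion in 1.2 also requires no trend in any other endpoint, so the rate under that rule is lower.
- A reader might infer that peak viral load, added after unblinded monitoring, was chosen for its treatment result. Amendment 3 gives an assay reason, and nothing shows that a comparison of arms drove the choice.

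**Conclusion.** The point holds as a gap in definition and reporting. Secondary trends count toward the conclusion without a criterion, the added p-values lack sidedness and a threshold and are not recorded as a change, and VL-AUC has no planned effect estimate with an interval.

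The size is conditional. If each secondary were read at one-sided 20%, the false-trend chance would be about 31–44% for three or four tests and 38–52% for six at correlations of 0.5–0.8, against 20% for the primary alone; 49–74% is only the independence bound. The 55–58% chance of detecting a 25% reduction rests on a gamma shape and on reading 320/275 as all placebo subjects. Those planning values come from a historical study with a different RT-PCR assay, and Figure 2 could not be seen. A null on the primary alone therefore cannot separate a modest effect from none. This should be fixed, but it does not invalidate the primary test.

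**What to change.** - In Protocol 1.2 and SAP 1.3 and 6.2.1, state that the formal trend and significance labels apply to RT-PCR VL-AUC only.
- In SAP 6.2.1, make the secondary p-values one-sided and label them supportive. List them in SAP Section 2 as a change from the descriptive analysis.
- Report the VL-AUC treatment difference, for example the difference in means and the Mann-Whitney probability, with two-sided 60% and 90% confidence intervals. Express the mean difference also as a percentage of the placebo mean, so that it can be set against the 50% used for sizing, and name in advance which interval governs the wording.
- Replace the negative conclusion in 1.2: a null is inconclusive unless that interval excludes a 50% reduction.

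The cost is wording and a few added outputs, with no new data. The real downside is fewer routes to a positive conclusion, and more missed modest effects if secondaries cannot count. The interval partly offsets this, because such a result would be reported as inconclusive and not as evidence against the model.
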